******MAIN RESEARCH QUESTIONS, STUDY AIMS, SPECIFIC HYPOTHESES******

1.1 Please clearly state your overall research questions and/or study aims.

Primary Outcome:

- 1) Is a fixed dose of 4-factor prothrombin complex concentrate (4FPCC) comparable to FDA-approved variable dosing for reversal of warfarin-induced anticoagulation (defined as an international normalized ratio [INR] ≤ 1.5) in patients with an INR ≥ 2 experiencing an emergent bleed or requiring emergent surgery?

Hypothesis: A fixed dose of 4FPCC will be comparable to FDA-approved variable dosing for reversal of warfarin-induced anticoagulation (defined as an international normalized ratio [INR] ≤ 1.5) in patients with an INR ≥ 2 experiencing an emergent bleed or requiring emergent surgery.

Secondary Outcomes:

- 1) What is the incidence of a thromboembolic event occurring within 7 days post-reversal with a fixed dose as compared to FDA-approved variable dosing of 4FPCC?

Hypothesis: The occurrence of a thromboembolic event within 7 days post-administration of a fixed dose of 4FPCC is lower than that of the FDA-approved variable dosing.

- 2) Does a fixed dose of 4FPCC provide significant cost-savings to the institution in dollars when compared to FDA-approved variable dosing?

Hypothesis: Utilizing a fixed dose of 4FPCC will provide for significant cost-savings to the institution as compared to FDA-approved variable dosing.

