The optimal dose of 4FPCC is currently unknown despite multiple studies evaluating different dosing regimens. The FDA-approved dosing is 25 to 50 IU factor IX per kilogram of body weight, depending on INR. It is dosed to a maximum of 100 kilograms of body weight. The FDA-approved variable dosing algorithm is as follows: initial INR 2-3.9: 25 IU/kg (maximum dose 2500 IU), initial INR 4-6: 35 IU/kg (maximum dose 3500 IU), and initial INR >6: 50 IU/kg (maximum dose 5000 IU) [6]. Exact doses of 4FPCC administered may vary slightly from the calculated doses as the amount of 4FPCC differs based on the vials utilized. There have been studies evaluating the use of fixed doses and variable doses utilizing body weight, body weight in combination with initial INR, body weight in combination with initial and target INR, and physician-chosen doses. Studies utilizing fixed doses or variable doses provided relatively good clinical and INR outcomes. Target INR outcomes were less achievable in studies utilizing physician-chosen doses [7]. Currently, many hospitals, including Regions Hospital, utilize the FDA-approved variable dosing based on body weight and initial INR to guide 4FPCC dosing to reverse warfarin-induced anticoagulation for patients presenting with emergent bleeding or requiring emergent surgery while on warfarin anticoagulation therapy. The FDA-approved dosing strategy is efficacious; however, its cost is significant to an institution. There were 67 cases of 4FPCC administration between January 2015 and May 2016 at Regions Hospital. The mean dose administered was 3021 IU (range 1000 IU to 7000 IU) and the average cost was \$7,236.17 (range \$2530 to \$17710) per dose... If clinically effective, a lower dosing strategy by means of a fixed dose may cost less than the FDA-approved variable dose. The lack of prospective studies evaluating fixed dosing regimens, especially in the United States, has hampered the emergence of fixed dosing as an optimal treatment regimen that is more cost effective. By performing a prospective study comparing a fixed dose and the FDA-approved variable dose, fixed dosing may be comparable to the FDA-approved dosing in emergent warfarin reversal. This could provide significant cost-savings to institutions and benefit patients in need of emergent anticoagulation.

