2.10 Describe your plans for ensuring data security

This study involves only minimum necessary data, in which only de-identified data will be reported. Data will be entered and stored in an HP secure RedCap database. All patients in the RedCap database will be identified only by their assigned study ID number. The database linking the patient MRN and ID number will be stored on a password-protected CCRC share drive that is only accessible to CCRC assigned staff. All electronic identifiers will be destroyed from Regions Hospital computers at the time of manuscript completion. There will not be paper data collection records for this study.

2.11. List the KEY variables that will be collected to support the study aims outlined in item 1.1. KEY variables include those used for:

- 1) achieving the study aims (outcomes, predictors, potential confounders),**
- 2) identifying the study population (for inclusion/exclusion criteria),**
- 3) describing the study population**

Please see an [Example of a Completed Table](#) and an [Example Data Dictionary](#).

Variable Name	Data Source (patient survey, EMR, claims, registry)	Purpose (sample identification, description, grouping variable, study endpoint, predictor, covariate)	Measurement Scale (binary, continuous)
Presenting INR (iSTAT and laboratory value)	EMR	Study endpoint	Continuous
Time of initial INR draw (iSTAT and laboratory value)	EMR	Variable	Continuous
INR at 15 minutes post-administration of 4FPCC	EMR	Study endpoint	Continuous
Dose of 4FPCC in IU	EMR	Study endpoint	Binary
Time to administration of 4FPCC in minutes	EMR	Study endpoint	Continuous
Administration of additional 4FPCC in fixed dose arm	EMR	Study endpoint	Binary
Thromboembolic events within 7 days	EMR	Study endpoint	Binary
Timing of thromboembolic event	EMR	Study endpoint	Continuous

Patient charge of 4FPCC in dollars	EMR	Study endpoint	Continuous
Institution cost of 4FPCC in dollars (cost per unit)	Biocare	Study endpoint	Continuous
Weight (kg) at presentation	EMR	Covariate	Continuous
Use of other reversal agents (vitamin K and FFP)	EMR	Covariate	Binary
Age	EMR	Covariate	Continuous
Indication for 4FPCC	EMR	Covariate	Binary
Attending Provider Specialty (i.e. emergency medicine, trauma, hematology/oncology, neurosurgery)	EMR	Covariate	Binary
Hospital unit (i.e. emergency department, SICU, MICU, etc.)	EMR	Covariate	Binary
Eligible patients not enrolled due to physician discretion	EMR	Covariate	Binary

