Cost outcomes will be assessed for all study patients and compared by dosing assignment. Generalized linear regression models will be constructed to estimate the difference in cost attributable to dosing assignment (β estimate), along with 95% confidence intervals and p-values. Specifications of the statistical models constructed will be dictated by the empirical distribution of cost outcomes, which we anticipate will be non-normal. In this case, the negative binomial distribution or other modeling assumptions may be used as appropriate.

Sample size:

3.2 What is the estimated sample size(s) for the primary study analyses (per group for studies with different arms or comparison groups)?

Preliminary data from Regions Hospital identified 67 patients treated with 4FPCC from January 2015 through May 2016, suggesting that we can expect about 4 eligible patients per month. Thus for a 1-year study we anticipate 48 patients in our study population, with approximately 24 patients in each dosing group. We will request approval to enroll up to 60 patients as more may present to the Emergency Department compared to our historical data.

3.3 The sample size selected was (check all that apply):

	Based on data likely to be available during a specific time period (often based on data available in past periods)
	To conduct one or more specific analyses with adequate statistical power
	To achieve a specified level of precision in one or more key estimates
	Other (explain):

3.4 Explain your choice of the sample size selection you listed above:

Sample size for this study will directly depend on the number of eligible patients on warfarin who present to the ED with bleeding emergencies during the study period.

3.5 Describe your assumptions concerning data available for analysis (e.g. How many subjects will be randomized, possibly lost to follow-up or a procedure? What do you expect for survey response rates, and how much missing data do you expect?). Include information as it pertains to your study (human or animal).

Our primary assumptions regarding available data include: 1) successful enrollment of eligible patients into the study; 2) complete data collection for relevant study variables; and 3) an even distribution of random assignment (1:1).

Missing data should be minimal, as the relevant clinical measures under evaluation are routinely documented in this context.

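### Aim 3 asks for a saving in dollars, but the only distribution named for non-normal costs is a count model whose usual coefficient is a log cost ratio, with no conversion to dollars and no variance method for unequal spread

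*Combined protocol and SAP*

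**What the plan says.** Section 1.1, secondary outcome 2, asks whether a fixed dose will "provide significant cost-savings to the institution in dollars when compared to FDA-approved variable dosing".

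Section 3.1 (Aim 3) answers with regression: "Generalized linear regression models will be constructed to estimate the difference in cost attributable to dosing assignment". The coefficient is given as that difference, with a 95% confidence interval and p-value. On the form of the model the plan says "Specifications of the statistical models constructed will be dictated by the empirical distribution of cost outcomes". It expects non-normal costs, in which case "the negative binomial distribution or other modeling assumptions may be used as appropriate".

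The key-variable table in section 2.11 lists two cost endpoints, both continuous and in dollars. One is "Patient charge of 4FPCC in dollars". The other is the institution's cost, recorded per unit. Section 3.1 does not say which is modelled. Nor does it give a link function, a conversion to dollars, a treatment of the dispersion parameter, or a variance method that allows the arms to differ in spread.

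**The concern.** Three things do not fit together.

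- **Scale.** A log-link coefficient is the log of a ratio of mean costs. Reported as the plan describes it, it would not be the dollar figure that section 1.1 asks for.
- **Type of variable.** The negative binomial describes counts. Cost is listed as continuous dollars.
- **Spread.** The negative binomial ties the variance in each arm to its mean through one shared dispersion. By design the arms differ sharply. The fixed arm receives 1500 IU, sometimes with a further 500 IU (section 2.7). Historical doses under variable dosing ran from 1000 to 7000 IU (section 1.2).

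The size of the saving and its interval are the whole output of Aim 3, and section 6.3 says the results will influence whether the hospital adopts fixed dosing. Choosing the model after seeing the costs adds a discretionary step. A two-arm randomized comparison does not need it, because the difference in mean cost is meaningful whatever the shape of the distribution.

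**Working it through.** The plan states no design figure for Aim 3, so there is nothing of its own to reproduce.

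**Inputs from the document**
- Historical cost under variable dosing: "average cost was \$7,236.17 (range \$2530 to \$17710) per dose" (section 1.2). No SD is given.
- Unit cost from the range end points: 2530/1000 = 17710/7000 = $2.53 per IU. The quoted means imply 7236.17/3021 = $2.40 per IU, so the two do not fully agree. This does not alter the conclusion.
- Fixed dose 1500 IU, with a possible additional 500 IU (section 2.7).
- 24 patients per arm (section 3.2).

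**Assumptions, not in the document**
- Variable-arm costs lognormal with SD $2,000 to $4,000.
- 5% vial-to-vial variation in the fixed arm.
- Additional dose given to 0% or 25% of the fixed arm.

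**Step 1: what the coefficient measures**
- No additional doses: fixed mean 1500 × 2.53 = $3,795. Difference 3795 - 7236 = -$3,441. Log ratio ln(3795/7236.17) = -0.645, a cost ratio of 0.52.
- 25% additional doses: fixed mean (1500 + 125) × 2.53 = $4,111. Difference -$3,125. Log ratio -0.565, a cost ratio of 0.57.

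**Step 2: can dollars be recovered?** Yes. In a two-arm model without covariates the fitted means equal the sample means. In one simulated data set exp(b0 + b1) - exp(b0) from the log-link fit and the raw mean difference were both -$3,162.92. An identity link gives that value directly as the coefficient.

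**Step 3: effect of a shared dispersion.** The model variance in an arm with mean m is m + a·m², with the same a in both arms. Take a variable-arm SD of $3,000 and no additional doses, where the average maximum-likelihood estimate was a = 0.0759.
- Implied SDs: about √0.0759 × 3795 = $1,046 in the fixed arm (assumed true value 0.05 × 3795 = $190) and √0.0759 × 7236 = $1,994 in the variable arm (assumed true value $3,000).
- Model SE of the dollar difference: √[(3795 + 0.0759 × 3795²)/24 + (7236 + 0.0759 × 7236²)/24] = $460.
- Correct SE: √[(3000² + 190²)/24] = $614.

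The model overstates the spread in the quiet arm and understates it in the noisy one. In dollars the noisy arm dominates, so the interval is too narrow.

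**Step 4: dispersion fixed at 1**
- Log-scale SE is about √(2/24) = 0.289 whatever the data.
- The interval for the cost ratio is exp(-0.645 ± 1.96 × 0.289) = 0.30 to 0.92, a saving of about $550 to $5,080 on a mean of $7,236.

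**Step 5: simulated coverage of nominal 95% intervals** (2,000 trials per setting, except Welch, which was run separately under the same range of assumptions)

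| Interval | Coverage |
|---|---|
| Dollar difference, estimated dispersion, model SE | 83-89% (SE 17-28% too small) |
| Dollar difference, dispersion fixed at 1 | about 100% (SE 2 to 4 times too large) |
| Dollar difference, robust SE | 91-94% |
| Dollar difference, Welch | 93-94% |
| Log ratio, estimated dispersion, model SE | 91-93% |

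**The case against.** The plan does not commit to this model. The negative binomial is an example that may be used, no link is stated, and the declared target, "to estimate the difference in cost attributable to dosing assignment", is the right one. With an identity link the coefficient is the dollar difference. All of that stands.

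A reader might infer two stronger things that the document does not support.

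- **That the model cannot estimate the dollar saving.** It can, exactly, in a two-arm fit (Step 2). What is missing is a stated link or conversion.
- **That its intervals are wrong in general.** The log-ratio interval with estimated dispersion is close to nominal, and a robust standard error largely repairs the dollar interval. The $550 to $5,080 interval arises only if dispersion is fixed at 1, which the plan nowhere says. It illustrates what the wording leaves open and does not predict what would be reported.

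The fixed arm is also not strictly constant. An additional 500 IU adds 500 × 2.53 = $1,265, and at an assumed 25% use the fixed-arm SD is about $560. The coverage figures already include that case.

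Finally, section 3.1 leaves room for covariate adjustment if baseline differences appear. A two-sample Welch interval cannot carry that, so Welch alone is not a complete replacement.

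What survives is that the text allows implementations whose dollar intervals differ widely in quality, and the one model it names fits this design poorly when used with its own standard errors.

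**Conclusion.** The concern holds in a conditional form. Section 3.1 calls the coefficient the difference in cost while naming, for the non-normal case it expects, only a count model whose usual coefficient is a log ratio. It specifies no conversion to dollars. If a dollar interval is then taken from the model's own standard errors, coverage of a nominal 95% interval is about 83-89% with estimated dispersion and about 100%, with far too wide an interval, when dispersion is fixed at 1. If the log ratio is reported with estimated dispersion, coverage is 91-93%, but the answer is not in dollars.

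These figures rest on the assumed variable-arm SD and lognormal shape, the 5% vial variation and the 0% or 25% additional-dose share. The document supplies none of these.

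It should be changed, but the stakes are limited. The aim is secondary, the primary conclusion is unaffected, and the direction of the saving is not in question. Its size and precision are.

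**What to change.** In section 3.1 (Aim 3), replace the model description with a prespecified estimate:

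- **Estimate:** the difference between arms in mean institutional 4FPCC cost per patient, in dollars, by assignment, counting any additional dose. This also settles which of the two cost variables in section 2.11 is primary.
- **Interval:** 95%, by Welch's method or a bootstrap.
- **If covariates are added under section 3.1:** an identity-link model, or a log-link model converted back to a dollar difference, with robust or bootstrap standard errors.
- **Negative binomial:** drop it as the named model. Keep any log-link model as a sensitivity analysis reported in dollars.

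The cost is a sentence or two of text. No new data are needed, since dose given and unit cost are already collected, and the main analysis becomes simpler than the one planned.

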******1. BACKGROUND & SIGNIFICANCE******

1.2 What is the specific knowledge gap that the project intends to fill? Include a brief review of past research in this area, numbering your citations to relevant literature as well as including them in the reference section #9.1.

Warfarin is a common oral anticoagulant utilized in the United States for the treatment and prevention of thromboembolic events and conditions. Although effective, the major complication associated with warfarin is the risk of major bleeding events. Incidence of major bleeding events in long-term warfarin users is 1.5% to 5.2% per year, with mortality exceeding 13%. Among patients with an intracranial bleed, the mortality rate increases to 46%-55% [1]. In these situations, it is imperative to reverse the pharmacologic effects of warfarin quickly in order to minimize bleeding and reduce the risk of death. Warfarin inhibits formation of vitamin K-dependent clotting factors II, VII, IX, X, and proteins C and S. An international normalized ratio (INR) is a commonly utilized laboratory test to measure the amount of anticoagulation

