Based on previous literature [D'Agostino 2003, Goldstein 2015] and the available study sample, we propose to set the non-inferiority margin M to -0.1. In other words, if the proportion of warfarin reversal among fixed dose patients is no worse than 10% less than the proportion of warfarin reversal among variable dosed patients, then we will reject the null hypothesis (superiority of variable dosing), and consider the fixed dose to be acceptably non-inferior to variable dosing.

Results to be reported for this aim will consist of the proportion of reversal for each group, the risk difference (RD; the proportion of reversal in fixed group minus the proportion of reversal in variable group), and the risk ratio (RR; the proportion of reversal in fixed group divided by the proportion of reversal in variable group), along with 95% confidence intervals and p-values as appropriate. Non-inferiority will be established if the lower bound of the RD is greater than the pre-specified margin M (-0.1). The primary analysis will use an intent to treat (ITT) approach (fixed vs. variable treatment assignment); however, we will also conduct supplemental analyses using an 'as treated' or 'per protocol' (PP) approach, in which we will compare patients' actual received dose (regardless of assignment) with respect to successful reversal of anticoagulation. We expect the PP approach to complement the primary ITT results, and will be informative particularly if there is non-trivial overlap in dosing by assignment group.

(Secondary) Aim 2: Fixed vs. variable dose 4FPCC and thromboembolic events

Study patients will be followed for 7 days post-administration of 4FPCC for thromboembolic events, as defined in Section 2.12. For this outcome, we will calculate and report the risk (proportion of patients experiencing an event in each group), RD, and RR, with 95% confidence intervals and p-values, as described in Aim 1. While we expect the risk of thromboembolic events to be lower in the fixed dose group, due to the limited number of anticipated thromboembolic events in the study population, the study will not specifically be powered to detect statistically significant differences by dosing group.

(Secondary) Aim 3: Fixed vs. variable dose 4FPCC and costs

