We also expect loss to follow-up to be minimal, as the observation period for a given patient is very short (INR can be evaluated within 15 minutes of 4FPCC administration), and it will be unlikely for patients to leave the hospital prior to collection of relevant measures during an emergency care situation. Though it is possible patients may die during hospitalization, sufficient information should be available for these individuals to contribute to the analysis, with the possible exception of Aim 2 (thromboembolic events).

Power analysis

NOTE: If you are doing a descriptive study (i.e., aside from computing confidence intervals you are not using statistical tests, inferential statistical testing for group comparisons, or statistical models), please complete 3.6 and skip 3.7-3.8.

If you are conducting statistical tests, using statistical inference to compare groups, or are building statistical models, please skip 3.6 and complete 3.7-3.8. **Please see our Example Power Analysis.**

3.6 Provide a measure of the precision of your estimates for key study endpoints, (e.g., 95% confidence intervals on proportions or means), using actual expected estimates.

N/A

3.7 What level of differences observed in your primary endpoints would be considered clinically or practically significant?

As dictated by the active-controlled non-inferiority approach, we will consider the fixed dose of 4FPCC to be non-inferior to variable dosing if the proportion of anticoagulation reversal is no worse than the specified difference margin of -10%.

3.8 What is the power for your primary analysis (and the set of assumptions underlying it: hypothesis addressed, expected pattern of effects with justification for these expectations, analysis used, variables in the analysis, effect sizes, sample sizes, alpha level, one or two-sided test)?

Assuming available treatment group samples of N=24, a non-inferiority margin of -0.1, an alpha significance level of 0.05, an expected targeted reversal proportion in the variable dosing group of 0.77 (pooled estimate from 13 previous studies) [Khorsand 2015], and a true difference in proportions of 0, we will have 22% power to detect non-inferiority of fixed vs. variable dosing of 4FPCC.

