8.10 Data Content (Please mark all content areas that apply to your study)

Mark (X)	Data Content
X	Demographic: age and gender

	Health Plan enrollment information (i.e., dates, coverage)
X	Diagnoses - Medical
X	Procedures - Medical
	Mortality Data
X	Lab Results
X	Prescriptions/ Medications
X	Dates of Service (treatment)
X	Facility or Provider Identifier / Characteristics (e.g., specialty, FTE, Clinic)
	Birth Certificate Data
	Pathology / Tissue Type
X	Financial data
X	Provider notes
X	Vitals – height, weight, BP, etc
	Social history – tobacco use, etc.
X	Other Clinical data
X	Other: please describe: the attending physician will be recorded

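### The plan foresees deaths before day 7, but no collection list shown records them and Aim 2 has no rule for counting patients who die

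*Combined protocol and SAP*

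**What the plan says.** - **Section 3.5 (data available for analysis).** The plan writes "Though it is possible patients may die during hospitalization", and continues that "sufficient information should be available for these individuals to contribute to the analysis, with the possible exception of Aim 2 (thromboembolic events"). No handling rule follows.
- **Section 3.1, Aim 2.** "Study patients will be followed for 7 days post-administration of 4FPCC for thromboembolic events". The measure is "the risk (proportion of patients experiencing an event in each group"), with a risk difference and risk ratio reported as for Aim 1. The denominator is not defined for patients who die. The same paragraph adds that "the study will not specifically be powered to detect statistically significant differences by dosing group".
- **Section 1.2 (background).** Major bleeding on long-term warfarin is described "with mortality exceeding 13"%. The text then states: "Among patients with an intracranial bleed, the mortality rate increases to 46%-55"%. Neither figure has a time frame. Intracranial haemorrhage is a named indication in section 2.3.
- **Collection lists.** None of the 13 steps in section 2.8 records death, date of death or vital status, and neither does the key-variable table in 2.11. Section 2.13, on further data elements, is answered N/A. In section 8.10 the "Mortality Data" box is unmarked, while many of its neighbours are marked. The state death data box in 8.7 is also unmarked.
- **Follow-up.** Section 2.7 provides for chart review each day of the admission and a reading of the last progress note inside the 7-day window. Section 3.9 gives discharge as the reason 7-day follow-up may be incomplete and does not mention death.

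**The concern.** Take a patient who dies on day 2 without a thromboembolic event. The last progress note dates from about day 2, and no listed field separates this patient from one who was alive and event-free at day 7. An analyst who follows the section 3.5 caveat may drop the patient. One who follows the Aim 2 text may keep the patient as a non-event. The plan does not choose between these, and the listed variables would not show how many such patients each arm had.

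The possible bias matters because of its direction. Section 1.1 predicts fewer thromboembolic events with the fixed dose. Death ends the opportunity for a later event, so an excess of early deaths in the fixed arm could look like support for that prediction.

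Thromboembolic events are also the only safety endpoint in the 2.11 table. The trial compares 1500 IU with a regimen whose mean dose at this hospital was 3021 IU (section 1.3), and its results are meant to influence whether the hospital adopts fixed dosing (section 6.3). As listed, it would report no deaths by arm.

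**Working it through.** The documents give no death rate, event rate or power for Aim 2, so there is no stated figure to reproduce. The steps below show what could happen under labelled assumptions.

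**1. How many deaths?** Inputs: 24 per arm (section 3.8), and 13% or 46% to 55% mortality (section 1.2). Assumption: these rates apply within follow-up. The 7-day counts would be lower if they describe a longer period.
- At 13%: 0.13 × 24 = 3.1 per arm, and 0.13 × 48 = 6.2 in total.
- P(at least one death among 48) = 1 − 0.87^48 = 99.9%.
- With equal true risk, the chance that the arms differ by three or more deaths is 28% (sum over two independent binomials, n = 24, p = 0.13).
- If every patient had an intracranial bleed: 0.46 × 24 = 11.0 to 0.55 × 24 = 13.2 per arm. If a quarter to three quarters did (assumed, so 6 to 18 per arm): 6 × 0.46 = 2.8 to 18 × 0.55 = 9.9 deaths among them.

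**2. How many events?** Aim 2 anticipates few, and section 1.3 reports none within 7 days in a retrospective 1500 IU cohort. At an assumed risk of 2% to 8%: 0.02 × 24 = 0.5 to 0.08 × 24 = 1.9 per arm. Early deaths could therefore equal or outnumber events.

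**3. Patients who die kept as non-events.** Assume equal event risk r while alive, with 6 deaths in one arm and 3 in the other.
- No risk time before death: RR = (18r/24)/(21r/24) = 18/21 = 0.86.
- Half of the 7-day risk accrued before death: RR = (18 + 3)/(21 + 1.5) = 21/22.5 = 0.93.
- At r = 8% and no risk time before death: 6.0% versus 7.0%. The difference of 1 point is 0.01 × 24 = 0.24 of a patient.
- Precision at that risk: 1.96 × √(2 × 0.08 × 0.92/24) = 0.15, a 95% half-width of about 15 points.

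**4. Patients who die dropped.** If event risk is unrelated to death, there is no bias. If some deaths follow thromboembolic events, dropping those patients also removes their events. An illustration with assumed counts, 24 per arm: in the fixed arm, 6 deaths, 2 of them after an event, and 1 event in survivors; in the variable arm, 3 deaths without an event, and 2 events in survivors.

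| Rule | Fixed | Variable | RD (points) | RR |
|---|---|---|---|---|
| Survivors only | 1/18 | 2/21 | −4.0 | 0.58 |
| All randomised, events before death counted | 3/24 | 2/24 | +4.2 | 1.50 |
| Event or death | 7/24 | 5/24 | +8.3 | 1.40 |

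In this constructed case, the sign depends on a rule the plan does not state.

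**The case against.** A reader might infer that the plan excludes patients who die, so that Aim 2 is conditional on survival, and that death is collected nowhere. The documents do not support either statement. Section 3.5 speaks of deaths as possible and of a possible exception; it is a remark about data availability, not an exclusion rule. Aim 2 refers to study patients and reports results as in Aim 1, where intention to treat is primary, so an all-randomised denominator is at least as natural a reading. The data collection form mentioned in section 2.6 is an attachment not available here, and part of the text between sections 3 and 5 is also missing, so a complete absence of mortality data cannot be confirmed. The unmarked box in 8.10 is weak evidence alone, because provider notes and other clinical data are marked and can show an in-hospital death.

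Three further arguments also carry weight:
- Daily chart review can capture an event charted before an in-hospital death. The survivors-only row in the illustration arises only if those patients are dropped.
- The direction of bias is not assured. Dropping patients who die is harmless when event risk is unrelated to death, and keeping them shifts the result by far less than the interval width.
- Under-reversal is assessed directly by the 15-minute INR and by additional dosing in the fixed arm.

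These arguments limit the size and certainty of the bias. They do not supply a denominator rule, or a listed field that separates an early death from event-free survival. INR and additional dosing do not report deaths by arm.

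**Conclusion.** The point holds as a gap in data collection and in the Aim 2 definition. The plan foresees deaths, lists no variable for them in any section shown, and does not say how they enter the 7-day comparison. The result could favour an arm with more early deaths, depending on the handling and on whether deaths are related to events.

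The size is uncertain. Roughly 3 deaths per arm rests on applying a 13% figure of unstated time frame. The risk ratios of 0.86 to 0.93 rest on an assumed 6 versus 3 deaths, and the change of sign rests on constructed counts. Aim 2 is secondary and unpowered, and the 15-minute INR endpoint is little affected. This is a cheap improvement to what the trial can say about safety; it does not undermine the primary analysis.

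**What to change.** - Add death within 7 days (yes/no) and its date to sections 2.8 and 2.11, taken from the daily chart review already planned, and mark the "Mortality Data" box in section 8.10.
- In Aim 2, state that all randomised patients are analysed by assigned arm, that thromboembolic events charted before death count, and that deaths by day 7 are reported by arm beside the thromboembolic risk. With complete 7-day follow-up, the risk with death as a competing event is simply events divided by all randomised, so no special estimator is needed.
- Replace the Aim 2 exception in section 3.5 with this rule.
- A composite of thromboembolic event or death is optional and supporting only, because it mixes deaths from the bleed with possible drug-related events.

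The cost is two data fields and one or two table rows. Treatment, sample size and the primary endpoint do not change.
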